Improving the Academic Performance of First-Grade Students with Reading and Math Difficulty

NCT03991234

Study Protocol and Statistical Analysis Plan

10/27/2025

Improving the Academic Performance of First-Grade Students with Reading and Math Difficulty

NCT03991234

Study Protocol

Summary: The main purpose of this clinical trial is to explore short-term effects of coordinated intervention versus the business-as-usual school program on the primary endpoints of post-intervention word-reading fluency and arithmetic fluency. The study population is students who begin 1st grade with delays in word reading and calculations. Students who meet entry criteria are randomly assigned to coordinated intervention across reading and math, reading intervention, math intervention, and a business-as-usual control group (schools' typical program). The 3 researcher-delivered interventions last 15 weeks (3 sessions per week; 30 minutes per session). Students in all 4 conditions are tested before researcher-delivered intervention begins and after it ends.

Eligibility: The student attends a participating school in the Metropolitan-Nashville Public Schools and is a member of a first-grade classroom whose teacher has agreed to let his/her students participate. The student must have the available school schedule to participate and adequate English proficiency to be reliably assessed in English on study entry screening measures. The student must score at or below the 25th percentile on the study's screening math test, score at or below the 25th percentile on the study's screening reading test, and score at or above the 7th percentile on at least one of the study's two measures of cognitive performance

Detailed Description: First-grade students who meet study entry criteria are identified near the start of the school year using a 3-stage screening process. Students who enter the study complete the pretest battery.

Then, students are randomly assigned at the individual level to coordinated intervention, reading intervention, math intervention, or a business-as-usual control group (the schools' typical classroom instruction with supplemental intervention schools choose to provide). Research staff deliver intervention in the coordinated intervention condition, in the reading intervention condition, and in the math intervention condition 1:1 for 15 weeks (three 30-min sessions per week, scheduled in line with teacher input to avoid students missing

important content). Adherence to the researcher-delivered interventions is monitored via audio recordings and live observations.

The content of each researcher-delivered intervention is aligned with the school district's 1st-grade foundational reading & math learning standards; relies on explicit instruction; and incorporates fluency-building activities word reading and/or arithmetic problems; incorporates procedures designed to build engagement and perseverance. Reading intervention is designed to build skill in letter-sound associations, decoding, sight words, and contextualized reading. Math intervention is designed to build number knowledge, counting strategies, and arithmetic skills. Coordinated intervention addresses the same instructional objectives as reading intervention & math intervention.

When researcher-delivered intervention ends, students in all four conditions complete the posttest assessment battery. Testers are blind to students' study conditions. Adherence to testing protocols is monitored via audio recordings. The primary endpoints are posttest word-reading fluency and arithmetic fluency.

Statistical Analysis Plan

For the analyses, we pooled data across the cohorts. Intra-class correlations (ICCs), indicating dependence due to clustering ranged from .010-.133 at the classroom-level (level-2) and from .001-.044 at the school-level (level-3). Therefore, for each outcome measure, we conducted fit a three-level multilevel model with students (level-1) nested within classrooms (level-2), nested within schools (level-3). For each model, we adjusted for pre-test performance at level-1 and cohort at level-2, and accounted for missing data using full information maximum likelihood estimation. All analyses were conducted in Mplus 8.4 (Muthen & Muthen, 1998-2025).

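### The analysis model has no term for the research tutor, who exists only in the three active arms; if tutors taught several students each and differ in effect, active-versus-control standard errors are too small

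*Combined protocol and SAP*

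**What the plan says.** **Allocation and delivery (Study Protocol, Detailed Description).** Allocation is by student: "students are randomly assigned at the individual level to coordinated intervention, reading intervention, math intervention, or a business-as-usual control group". For the active arms, "Research staff deliver intervention in the coordinated intervention condition, in the reading intervention condition, and in the math intervention condition 1:1 for 15 weeks". The control arm receives "the schools' typical classroom instruction with supplemental intervention schools choose to provide", so it has no research tutor.

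**Main contrast (Study Protocol, Summary).** The main purpose is to "explore short-term effects of coordinated intervention versus the business-as-usual school program", on two primary endpoints: word-reading fluency and arithmetic fluency after intervention.

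**Model (Statistical Analysis Plan).** The levels are justified by ICCs that "ranged from .010-.133 at the classroom-level (level-2) and from .001-.044 at the school-level (level-3". The model is a "three-level multilevel model with students (level-1) nested within classrooms (level-2), nested within schools (level-3". On covariates, "we adjusted for pre-test performance at level-1 and cohort at level-2". Missing data are handled by full information maximum likelihood.

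The plan mentions no tutor random or fixed effect, no tutor-clustered standard error and no tutor ICC. It does not give the number of tutors, their caseload, how they were assigned across arms and schools, or whether a student kept one tutor throughout.

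**The concern.** Students who share a tutor share that tutor's skill, pace and rapport over 15 × 3 = 45 sessions, so their outcomes may be correlated. This correlation can arise only in the active arms. Classroom and school intercepts are common to treated and control students and cannot represent an effect that only treated students have. Pre-test adjustment cannot remove it either, because it arises after pre-test.

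In coordinated versus BAU, tutor variation therefore sits wholly on one side of the contrast. A model that treats treated students as independent, given classroom and school, counts them as more information than they are. The confidence interval is then too narrow and the test rejects too often. This would touch the main contrast on both primary endpoints.

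The plan's own reasoning points the same way. It justifies its levels by measured dependence, including a school-level ICC as low as .001, but reports no corresponding measurement for tutors.

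**Working it through.** **No figure to reproduce.** The documents state no sample size, alpha, effect size or standard deviation for this contrast, so the check gives the size of the effect under stated assumptions.

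**Inputs from the documents:** individual allocation to four arms; one-to-one delivery by research staff in three arms only; a model with classroom and school intercepts, pre-test and cohort.

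**Assumptions, none given in the documents:** m = students per tutor within the arm, 3 to 8; ρ = tutor ICC, 0 to 0.10; equal arms with equal total variance; one tutor per student; two-sided test at a nominal 5%.

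**Formulas**
- Design effect in the tutored arm: DE = 1 + (m − 1)ρ. For BAU it is 1.
- True SE ÷ reported SE: R = √[(DE + 1)/2].
- Shortfall in the reported SE: 1 − 1/R.
- Actual type I error: 2 × [1 − Φ(1.96/R)].

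**Results**

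| m | ρ | DE | R | Reported SE too small by | Type I error |
|---|---|---|---|---|---|
| any | 0 | 1.00 | 1.000 | 0% | 5.0% |
| 3 | 0.02 | 1.04 | 1.010 | 1.0% | 5.2% |
| 5 | 0.05 | 1.20 | 1.049 | 4.7% | 6.2% |
| 5 | 0.10 | 1.40 | 1.095 | 8.7% | 7.4% |
| 8 | 0.05 | 1.35 | 1.084 | 7.7% | 7.1% |
| 8 | 0.10 | 1.70 | 1.162 | 13.9% | 9.2% |

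Worked line for m = 5, ρ = 0.05: DE = 1 + 4 × 0.05 = 1.20; R = √(2.20/2) = 1.049; shortfall = 1 − 1/1.049 = 4.7%; type I error = 2 × [1 − Φ(1.96/1.049)] = 6.2%.

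Outside the assumed range, m = 12 with ρ = 0.15 gives R = 1.351 and a type I error of 14.7%.

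**Do the modelled levels absorb it?** The formula ignores classrooms and schools, so a small simulation fitted the student, classroom and school model to data with a tutor effect in the active arms only. It used 400 replicates per setting and assumed 20 schools, 4 classrooms per school, 4 students per classroom, classroom variance 0.07, school variance 0.02 and residual variance 0.91. With four arms, one tutor per school means about 16/4 = 4 students per arm per tutor; one tutor per two schools means about 8.

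| Tutor variance | R, one tutor per school (rejection rate) | R, one tutor per two schools (rejection rate) |
|---|---|---|
| 0 | 0.97 (3.3%) | 1.01 (4.8%) |
| 0.05 | 1.03 (5.8%) | 1.13 (8.0%) |
| 0.10 | 1.10 (7.2%) | 1.22 (10.7%) |
| 0.15 | 1.12 (6.0%) | 1.30 (14.0%) |

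Monte Carlo error on R is roughly 3% to 4%, so the smallest departures from 1 are not decisive individually. The pattern is clear: R is about 1 without tutor variance and rises with tutor variance and caseload. Classroom and school intercepts do not remove the problem. Tutors moving at random across schools were not evaluated.

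**The case against.** The strongest reply is that the size is unknown and may be nil. The documents do not say that a tutor taught several students, or that a student kept one tutor. Adherence was monitored by recording and observing sessions, which favours uniform delivery and perhaps a small tutor variance. With tutor ICC near zero, very small caseloads or tutors rotating across students, the current standard errors are adequate. This stands, and it is why the point is conditional and the range starts at zero. It does not excuse leaving the quantity unmeasured.

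Three stronger readings are tempting but unsupported:

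- A reader might infer that tutors deliver all of the treated students' instruction. The protocol gives them three 30-minute sessions a week, timed to spare key classroom content; ordinary teaching continues.
- A reader might infer that randomisation was within classrooms, so that classroom and school effects cancel and the plan models the less important clustering. The protocol says only that allocation was by student and states no blocking by classroom. With classroom ICCs observed up to .133 and no tutor ICC reported, ranking the two is conjecture.
- A reader might read R = 1.162 as a reported SE that is 16% too small. The true SE is 16% larger; the reported one is 13.9% too small.

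It can also be said that the plan is written in the past tense with observed ICCs, so replacing the primary model now would be a post hoc change. This too has force and shapes the fix.

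**Conclusion.** The omission is real and its direction is certain once two conditions hold: tutors taught more than one student in an arm, and tutor variance is above zero. The documents establish neither, so they do not support a flat statement that the standard errors are too small.

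Under the assumptions above, the true active-versus-BAU standard error is 1.00 to 1.16 times the reported one, and the actual type I error is 5.0% to 9.2%; the mid-case is 1.049 and 6.2%. The effect is modest over most of that range, but it falls on the main contrast and both primary endpoints, and nothing else in the plan corrects it.

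The conclusion concerns active-versus-BAU contrasts. If tutors served several active arms, contrasts between active arms could be affected differently.

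**What to change.** For both primary endpoints, fit a partially nested (or cross-classified) model with a tutor random effect that applies only in the three research-delivered arms and is zero for BAU. Keep the pre-test and cohort adjustment and the likelihood-based handling of missing data.

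Report the number of tutors, caseload, assignment across arms and schools, whether students changed tutor, and the estimated tutor variance. Where that variance is not negligible, base the active-versus-BAU intervals on this model. Since the analyses appear to be done, the minimum is to report it as a sensitivity analysis, labelled as such, beside the current model.

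**Cost.** The models must be re-run with tutor identifiers. Sessions were recorded and observed, so these may be recoverable, but the documents do not confirm that they are held as data. A different estimator may be needed, and its handling of missing data should be checked against the present approach. Confidence intervals may widen slightly. If tutor variance proves negligible, the current results stand with better support.

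### As described, FIML gives the complete-case treatment estimate, so missing posttests must be random given condition, pretest and cohort; adding baseline scores already collected would cheaply relax that condition

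*Combined protocol and SAP*

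**What the plan says.** The missing-data plan is one clause of the Statistical Analysis Plan: the analysts "accounted for missing data using full information maximum likelihood estimation". The model it applies to is described just before: "for each outcome measure, we conducted fit a three-level multilevel model", with students within classrooms within schools, and "we adjusted for pre-test performance at level-1 and cohort at level-2". The condition contrasts are implied but not written out. No auxiliary variable, joint outcome model, missing-data assumption, attrition count or sensitivity analysis is named.

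On timing, the Study Protocol's Detailed Description says "Students who enter the study complete the pretest battery", and randomisation follows. The Summary adds "Students in all 4 conditions are tested before researcher-delivered intervention begins and after it ends", so there is one posttest occasion. "The primary endpoints are posttest word-reading fluency and arithmetic fluency". Entry also requires two screening tests (reading and math) and two cognitive measures, so these scores exist before randomisation.

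**The concern.** If the pretest battery is done before randomisation and there is a single posttest occasion, missing values should fall mainly on the posttest. In a model with one posttest as its only outcome, FIML has no second outcome or auxiliary variable through which to use a student who lacks that posttest. A reader who sees FIML named may assume that such students still inform the treatment effect. On the analysis as described, they do not.

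What is at stake is the assumption behind the estimates. If posttest absence is related to a score that was collected but is not in the model, and the relation differs by arm, the estimate can be biased even though the data are missing at random given everything collected.

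**Working it through.** The documents give no sample size, attrition or effect size, so there is no stated figure to reproduce. The check has three parts.

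**1. Algebra.** Write y for the posttest, x for the pretest and z for condition and cohort. The likelihood factors as f(y, x | z) = f(y | x, z; θ) · f(x | z; φ), and the treatment effect lies in θ. For a student with y missing and x and z observed, the first factor integrates to 1. What remains involves only φ. The same holds with random intercepts, because each student's mean depends on that student's own covariates, and dropping a missing y from the multivariate normal leaves the distribution of the observed ones unchanged.

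**2. Numerical check of the identity.**

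- Three-level model: 12 schools × 4 classrooms × 6 students = 288 students and four arms. Assumed ICCs are .10 (classroom) and .03 (school), inside the SAP's reported ranges of .010 to .133 and .001 to .044. Posttests are missing for 25.3%, depending on pretest.
- Complete-case ML: fixed effects 0.10640, 0.69937, 0.18076, 0.01167, 0.02341, −0.11973; variance components 0.43360, 0.07562, 0.05548.
- FIML on all 288 rows: the same values to five decimals. The largest difference in any fixed effect is 1.07e-7.
- A single-level check with 200 students, 174 of them observed, gave a treatment coefficient of 0.038893 by both methods.

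**3. What the shared estimate protects against.** Assumed design: two arms, 400 students, single level, 1,500 runs, true effect 0.30 SD, pretest slope 0.6. The auxiliary is always observed and correlates 0.6 with the posttest residual. In this simulation it also carries a treatment effect, so it behaves like another posttest, not like a baseline score.

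| Dropout depends on | Missing | Raw completer difference | Stated model | With auxiliary |
|---|---|---|---|---|
| Pretest, opposite direction by arm | 7.3% | 0.222 | 0.304 | 0.303 |
| | 13.5% | 0.154 | 0.300 | 0.300 |
| | 23.8% | 0.053 | 0.299 | 0.298 |
| Auxiliary, one arm only | 6.1% | 0.251 | 0.274 | 0.299 |
| | 11.8% | 0.207 | 0.250 | 0.297 |
| | 21.9% | 0.143 | 0.216 | 0.297 |
| Unseen posttest, one arm only | 6.1% | 0.237 | 0.259 | 0.274 |
| | 11.7% | 0.180 | 0.221 | 0.247 |
| | 21.9% | 0.096 | 0.169 | 0.216 |

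Monte Carlo error is about 0.09/√1500 = 0.002. In the first block the stated model is essentially unbiased. In the second its bias is 0.30 − 0.274 = 0.026, 0.30 − 0.250 = 0.050 and 0.30 − 0.216 = 0.084 SD, and the auxiliary removes nearly all of it. In the third the auxiliary helps only in part: at 21.9% missing, bias falls from 0.131 to 0.084 SD.

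A second simulation is closer to the proposed fix because the omitted variable is a baseline cognitive score. Assumptions: 100 per arm; outcome weights 0.5 (pretest) and 0.3 (cognitive score); true effect 0; 15–21% missing in the treated arm and 10–16% in the control arm, related to the cognitive score differently by arm; 3,000 trials in each of four scenarios.

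| | Bias, four scenarios (SD) | Empirical SE |
|---|---|---|
| Stated model | 0.035, 0.069, 0.043, 0.060 | 0.120–0.123 |
| Cognitive score added | 0.001, 0.000, −0.003, 0.003 | 0.113–0.117 |

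Relative to the standard error, the bias lies between 0.035/0.123 = 0.28 and 0.069/0.120 = 0.58. A further simulation with assumed mechanisms gave 0.02 to 0.08 SD, falling below 0.003 SD once the baseline scores were included.

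**The case against.** A reader might infer that the SAP's missing-data statement is untrue and that the trial has no protection against attrition. The documents do not support that. The sentence names an estimation method and promises no particular protection. A likelihood analysis conditional on condition, pretest and cohort is valid under missingness at random given those variables, if the outcome model is correct. The first block of the first table shows the adjustment working where the raw completer difference is badly off. This objection stands in full. What remains is that the protection comes from the covariates, so a complete-case analysis has it too.

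Other objections stand in part:

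- **Silence is not exclusion.** The SAP is one paragraph. Its pretest term is undefined and could cover more than the same-domain pretest, and a joint model or auxiliaries are not expressly ruled out. The point therefore applies to the analysis as described.
- **Pretest completeness is inferred** from a procedural sentence, and the protocol describes posttesting in similar terms. If some pretests are missing and the pretest is modelled, FIML does recover those rows. The identity could also be inexact if the pretest is split into latent within- and between-cluster parts, which was not tested.
- **The magnitudes are built from assumptions.** Making dropout depend on an omitted predictor differently by arm guarantees bias. The simulations show what could happen, not what did.
- **Joint modelling of the two primary posttests may do little.** Both belong to one battery on one occasion, and a student who misses both adds nothing to a joint likelihood.
- **The SAP is in the past tense.** Replacing the fitted model now could mean re-specifying it after seeing results.

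**Conclusion.** The point holds in a limited form. On the natural reading (one posttest per model, covariates observed, no auxiliaries), naming FIML adds nothing for missing posttests. The treatment estimate is the complete-case one and relies on missingness at random given condition, pretest and cohort.

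Simulated bias is about 0.02 to 0.08 SD when dropout is arm-specific and tied to an omitted score. It is essentially nil when dropout depends only on variables in the model. Which case applies here cannot be judged, because the documents give no attrition overall or by arm. It would be wrong to conclude that the trial's estimates are biased.

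This is a cheap improvement: scores already collected can widen the set of variables on which missingness may depend, with a small gain in precision in simulation.

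**What to change.** Add the baseline scores already collected to each outcome model, as level-1 covariates or as auxiliary variables in the FIML likelihood: pretests in both domains, the reading and math screening scores, and the two cognitive measures. If results are already known, keep the fitted model and report this one beside it as a labelled additional analysis.

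In the SAP, state the missing-at-random assumption, say what the pretest term contains and whether any auxiliaries were used, and report posttest attrition by arm.

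Two additions are optional. A joint model of the two primary posttests helps only students with one of them observed. A delta-shift sensitivity analysis would address dropout that depends on the unseen score, which auxiliaries correct only in part.

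The cost is a re-run on existing data with a somewhat larger model and possible convergence problems. No new data collection is needed.
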